### 5 POPULATIONS ANALYZED

For the purposes of this study, randomization (i.e., treatment assignment to left or right side of the face) is achieved by assigning available treatment kit IDs, in increasing sequential order, at the time subjects are confirmed to fully qualify for the study. This study will not use IRT technology to generate a randomization record.

# 5.1 Intent-to-Treat Population

The Intent-to-Treat (ITT) population is defined as all randomized subjects and will be used for the analyses of efficacy endpoints on the face. Subjects of the ITT population will be summarized and analyzed according to the treatment they were randomized to.

### 5.2 Per Protocol Population

The Per Protocol (PP) population is defined as comprising the ITT population subjects who are compliant to the treatment application (i.e. with an overall compliance between 80% - 120% inclusive), whose Baseline and Week 24 total atrophic acne scar counts are performed and who have no major deviations from the protocol that could have a significant effect on the efficacy of the study treatment (e.g. errors in treatment assignment, use of prohibited medications).

# 5.3 Safety Population

The Safety (SAF) population is defined as comprising the ITT population subjects who applied/took the study drug) at least once and will be used for all safety analyses. Subjects of the Safety population will be summarized according to the treatment they actually received.

### 6 STATISTICAL METHODS AND DATA CONSIDERATIONS

### **6.1** General Considerations

### 6.1.1 Baseline

For statistical analyses purpose, baseline is defined as the last non-missing measurement prior to the first treatment for subjects treated and as the last non-missing measurement prior to randomization for subject randomized but not treated.

Absolute change from baseline and percent change from baseline will be calculated as follows:

Absolute Change from Baseline - PostBaseline - Baseline

$$Percent \ Change \ from \ Baseline = \begin{cases} Baseline \neq 0 \Rightarrow 100 \cdot \frac{PostBaseline - Baseline}{Baseline} \\ Baseline = 0 \Rightarrow Missing \end{cases}$$

# 6.1.2 Missing and Partial Dates Management

- Start Date Imputation of Adverse Events:
  - Imputation of adverse event end date has to be done before imputation of event start date.
  - Completely missing: For subjects treated, impute to the first treatment date. For subject randomized but not treated, impute to the randomization date. For subjects not randomized, impute to the date of informed consent.
  - Missing day and month: For subjects treated, impute to January 1st, unless year is the same as year of first treatment dose then impute to the first treatment date. For subject randomized but not treated, impute to January 1st, unless year is the same as year of randomization then impute to the randomization date. For subjects not randomized, impute to January 1st, unless year is the same as year of informed consent then impute to the informed consent date
  - Missing day: For subjects treated, impute to the 1st of the month, unless month and year are the same as month and year of first treatment dose then impute to the first treatment date. For subject randomized but not treated, impute to the 1st of the month, unless month and year are the same as month and year of randomization then impute to the randomization date. For subjects not randomized, impute to the 1st of the month, unless month and year are the same as month and year of informed consent then impute to the informed consent date
  - If imputed event start date is after event end date (imputed or not), set the event start date to the imputed event end date.
- Start Date Imputation of Prior/Concomitant Therapies and Medical/Surgical Procedures:
  - Imputation of therapy/procedure end date has to be done before imputation of

Approved

therapy/procedure start date.

- Completely missing: For subjects treated, impute to the first treatment date. For subject randomized but not treated, impute to the randomization date. For subjects not randomized, impute to the date of informed consent.
- Missing day and month: For subjects treated, impute to January 1st, unless year is the same as year of first treatment dose then impute to the first treatment date. For subject randomized but not treated, impute to January 1st, unless year is the same as year of randomization then impute to the randomization date. For subjects not randomized, impute to January 1st, unless year is the same as year of informed consent then impute to the informed consent date
- Missing day: For subjects treated, impute to the 1st of the month, unless month and year are the same as month and year of first treatment dose then impute to the first treatment date. For subject randomized but not treated, impute to the 1st of the month, unless month and year are the same as month and year of randomization then impute to the randomization date. For subjects not randomized, impute to the 1st of the month, unless month and year are the same as month and year of informed consent then impute to the informed consent date.
- If imputed therapy/procedure start date is after therapy/procedure end date (imputed or not), set the therapy/procedure start date to the imputed therapy/procedure end date.
- Start Date Imputation of Medical History Diseases:
  - Imputation of disease end date has to be done before imputation of disease start date.
  - Completely missing: Leave it missing.
  - Missing day and month: Impute to January 1st.
  - Missing day: Impute to the 1st of the month.
  - If imputed disease start date is after disease end date (imputed or not), set the disease start date to the imputed disease end date.
- End Date Imputation of Adverse Events, Prior/Concomitant Therapies and Medical/Surgical Procedures, Medical History Diseases:
  - Completely missing and with outcome 'Not Recovered/Not Resolved' or 'Unknown' (Adverse Events): Leave it missing.
  - Completely missing and flagged as being ongoing (Prior/Concomitant Therapies and Medical/Surgical Procedures, Medical History Diseases): Leave it missing.
  - Completely missing and with an outcome different from 'Not Recovered/Not Resolved' and 'Unknown' (Adverse Events): Impute to the last contact date.
  - Completely missing and not flagged as being ongoing (Prior/Concomitant Therapies and Medical/Surgical Procedures, Medical History Diseases): Impute to the last contact date.
  - Missing day and month: Impute to December 31st, unless year is the same as last contact date then impute to the last contact date.
  - Missing day: Impute to the last day of the month, unless year and month are the same as

year and month of last contact date then impute to the last contact date.

### 6.1.3 Reference Start Date and Analysis Day

For subjects treated, the first treatment date will be the reference start date. For subject randomized but not treated, the randomization date will be the reference start date. For subjects not randomized, the reference start date will be set to missing.

Analysis day will be calculated from the reference start date and will be used to show start/end day of assessments, events, diseases, therapies or procedures.

In the situation where the assessment/event/disease/therapy/procedure date is fully missing and cannot be imputed (i.e. when an adverse event has outcome 'Not Recovered/Not Resolved' or 'Unknown' and when a disease, therapy or procedure is reported as being ongoing), analysis day will be missing.

### 6.1.4 Descriptive Statistics

For the descriptive statistics, unless otherwise noted, the categorical variables will be summarized by frequencies and proportions expressed as percentages (n, %) of subjects for each classification category and the continuous variables will be summarized using standard descriptive statistics (n, mean, standard deviation, median, first and third quartile, min and max).

### 6.1.5 Statistical Tests and Confidence Intervals

A two-sided type I error  $\alpha = 0.05$  will be used to declare statistical significance for the primary endpoints and the secondary endpoints. Confidence intervals (CIs) will be two-sided with 95% coverage for the primary endpoint and the secondary endpoints. The following flagging conventions will be applied for the p-values of all statistical testing:

- $0.01 \le \text{p-values} < 0.05 \text{ will be flagged with one asterisk (e.g. "0.0499 *")}$
- $0.001 \le \text{p-value} \le 0.01$  will be flagged with two asterisks (e.g. "0.0099 \*\*")
- $0.0001 \le \text{p-value} < 0.001 \text{ will be flagged with three asterisks (e.g. "0.0009 ***")}$
- p-value < 0.0001 will be flagged with four asterisks (e.g. "< 0.0001 \*\*\*\*")

### 6.1.6 Decimal Precision

Unless otherwise noted, the following rounding conventions will be applied:

- means, medians, first and third quartiles will be rounded and presented to one more decimal digit than the source data;
- confidence intervals of means and medians will be rounded and presented to one more decimal digit than the source data;
- standard deviations and standard errors will be rounded and presented to two more decimal digits than the source data;

- minima and maxima will be presented to the same number of decimal digits as the source data;
- proportions will be reported as percentages (not as fraction of unit);
- percentages greater than or equal to 0.1 will be rounded and presented to one decimal digit, percentages lower than 0.1 and greater than 0 will be presented as '<0.1', percentages equal to 0 will not be presented;
- confidence intervals of percentages will be rounded and presented to one decimal digit;
- standard errors of percentages will be rounded and presented to two decimal digits;
- p-values greater than or equal to 0.0001 and lower than or equal to 0.9999 will be rounded and presented to fourth decimal digits;
- p-values lower than 0.0001 will be presented as '< 0.0001';
- p-values greater than 0.9999 will be presented as '> 0.9999';

### 6.1.7 Software Version

All analyses will be performed using SAS® software Version 9.4 or higher.

### 6.2 Study Subjects

### 6.2.1 Disposition of Subjects

Frequencies and proportions (n, %) of subjects will be summarized for the following categories:

- Subjects screened
- Screen failures/not randomized subjects
  - Reason for screen failure/not randomized
- Screen failures/not randomized subjects due to COVID-19
  - Reason for screen failure/not randomized due to COVID-19
- Subjects randomized
- Subjects randomized who discontinued before treatment
  - Reasons for study discontinuation before treatment
- Subjects randomized who discontinued before treatment due to COVID-19
  - Reasons for study discontinuation before treatment due to COVID-19
- Subjects randomized who underwent the treatment
- Subjects randomized who completed the treatment
- Subjects randomized who discontinued the treatment
  - Reasons for treatment discontinuation
- Subjects randomized who discontinued the treatment due to COVID-19

CD5789.SPR202395.SAP.V02 - Final Version 27F

- Reasons for treatment discontinuation due to COVID-19
- Subjects randomized who completed the study
- Subjects randomized who discontinued the study
  - Reasons for study discontinuation
- Subjects randomized who discontinued the study due to COVID-19
  - Reasons for study discontinuation due to COVID-19
- Subjects randomized affected by COVID-19 related study disruptions
- Subjects randomized affected by COVID-19 related study disruptions impacting efficacy
- Subjects randomized affected by COVID-19 related study disruptions impacting safety

Listing for subjects' disposition, screen failures, discontinued subjects, treatment completion status, discontinued treatment and subjects affected by COVID-19 related study disruptions will be provided.

### 6.2.2 Accounting of Subjects

Frequencies and proportions (n, %) of subjects will be summarized in the ITT population for each clinical visit and each analysis visit.

Listings for subject scheduled visits and subject unscheduled visits will be provided.

### 6.2.3 Protocol Deviations

Major protocol deviations, major protocol deviations leading to the exclusion from the PP population, major protocol deviations due to COVID-19 and minor protocol deviations will be summarized using frequencies and proportions (n, %) of subjects in the ITT population for each deviation coded term by treatment side (trifarotene 50  $\mu$ g/g versus vehicle) and overall.

Local protocol deviations (localized to right or left side) will be presented by treatment side (trifarotene 50  $\mu$ g/g versus vehicle) and overall. Protocol deviations that are subject specific will be presented overall only.

A listing of all protocol deviations will be provided.

### 6.2.4 Data Sets Analyzed

Frequencies and proportions (n, %) of subjects in each analysis population (ITT, PP, SAF) will be summarized.

Frequencies and proportions (n, %) of subjects will be summarized for each inclusion/exclusion criterion not met.

Listings for inclusion/exclusion criteria not met and analysis populations will be provided.

# 10-Jul-2023 00:00:00

### 6.2.5 **Demographic and Other Baseline Characteristics**

Descriptive statistics (n, mean, standard deviation, median, first and third quartile, min and max) or frequencies and proportions (n, %) of subjects for each classification category (as applicable) will be presented using the ITT population for the following demographic data and baseline characteristics:

- Age (years)
- Age Groups
  - <18 years old
  - ≥18 years old
- Sex
  - Male
  - Female
- Ethnicity
  - Hispanic or Latino
  - Not Hispanic or Latino
  - Not Reported
- Race
  - White
  - Black or African American
  - Asian
  - American Indian or Alaska Native
  - Native Hawaiian or Other Pacific Islander
  - Other
  - Multiple
- Body weight at Screening (kg)
- Fitzpatrick Skin Type
  - Type I
  - Type II
  - Type III
  - Type IV
  - Type V
  - Type VI

- Baseline Investigator Scar Global Assessment (SGA) by treatment side (trifarotene 50 μg/g versus vehicle)
  - 0 Clear
  - 1 Almost Clear
  - 2 Mild
  - 3 Moderate
  - 4 Severe
- Baseline Total Atrophic Acne Scar Counts by treatment side (trifarotene 50 μg/g versus vehicle)
- Baseline 2-4 mm Atrophic Acne Scar Counts by treatment side (trifarotene 50 μg/g versus vehicle)
- Baseline >4 mm Atrophic Acne Scar Counts by treatment side (trifarotene 50 μg/g versus vehicle)
- Baseline Investigator Global Assessment (IGA) by treatment side (trifarotene 50 μg/g versus vehicle)
  - 0 Clear
  - 1 Almost Clear
  - 2 Mild
  - 3 Moderate
  - 4 Severe
- Baseline Total Lesion Counts by treatment side (trifarotene 50 μg/g versus vehicle)
- Baseline Inflammatory Lesion Counts by treatment side (trifarotene 50 μg/g versus vehicle)
- Baseline Non-Inflammatory Lesion Counts by treatment side (trifarotene 50 μg/g versus vehicle)

If ITT population and Safety population do not include the same subjects, the summary will be presented for the Safety population too.

Frequencies and proportions (n, %) of subjects will be summarized using the ITT population (females only) for the following classification category:

- Childbearing Potential
  - Strict Abstinence
  - Male/Female Condom
  - Cap, Diaphragm or Sponge with Spermicide
  - Combined (estrogen and progestogen containing) Oral, Intra-vaginal or Transdermal Hormonal Contraception

- Injectable or Implanted Hormonal Contraception
- Intra-Uterine Devices
- Vasectomized partner for at least 3 months prior to the Screening visit
- Other
- Non-childbearing Potential
  - Post-Menopausal
  - Hysterectomy or Bilateral Oophorectomy
  - Pre-Menses

Listings for demographic data, baseline characteristics and childbearing potential status (inclusive of methods of contraception and reproductive status) will be provided.

### 6.2.6 Medical History, Prior and Concomitant Therapies and Procedures

For statistical analysis purposes, prior therapies/procedures are defined as those ending before the first treatment day; concomitant therapies/procedures are defined as those starting before the first treatment day and ongoing on the first treatment day and as those starting on the first treatment day or after. If a subject does not undergo treatment, all therapies/procedures of that subject will be classified as prior.

Previous and concomitant therapies/medications will be coded using WHO Drug Dictionary (March 2021, B3 format). Medical history diseases and prior and concomitant medical/surgical procedures will be coded using MedDRA dictionary (version 24.0).

Summaries will be presented overall using the ITT population for the following:

- Frequencies and proportions (n, %) of subjects who had medical history diseases by System Organ Class and Preferred Term;
- Frequencies and proportions (n, %) of subjects who had prior therapies/medications by ATC levels 2, 3 and Active Ingredient(s);
- Frequencies and proportions (n, %) of subjects who had concomitant therapies/medications by ATC levels 2, 3 and Active Ingredient(s);
- Frequencies and proportions (n, %) of subjects who had prior medical/surgical procedures by System Organ Class and Preferred Term;
- Frequencies and proportions (n, %) of subjects who had concomitant medical/surgical procedures by System Organ Class and Preferred Term

Listings of all medical history diseases, prior and concomitant therapies/medications and medical/surgical procedures will be provided.

### **6.2.7 Measurements of Treatment Compliance**

### **6.2.7.1** Study Duration and Treatment Duration

For randomized subjects who discontinued before treatment, study duration will be calculated as date of end of participation minus date of randomization plus one (1).

For randomized subjects who underwent treatment, study duration will be calculated as date of end of participation minus date of first treatment plus one (1).

Study duration will be summarized for all patients in the ITT population using descriptive statistics (n, mean, standard deviation, median, first and third quartile, min and max).

Treatment duration will be calculated as date of last treatment minus date of first treatment plus one (1) and will be summarized using descriptive statistics (n, mean, standard deviation, median, first and third quartile, min and max) by treatment side (trifarotene 50  $\mu$ g/g versus vehicle) and overall in the ITT population.

Listings presenting study duration and treatment duration will be provided.

### 6.2.7.2 Compliance and Drug Accountability

For both trifarotene 50  $\mu$ g/g and vehicle, treatment compliance will be calculated as follows:

 $\label{eq:compliance} Treatment\ Compliance = 100 \frac{Actual\ Applications}{Planned\ Applications - Missed\ Applications\ due\ to\ Prescribed\ Dose\ Reductions}$ 

Planned applications are calculated as the number of days between start date and stop date of each compliance evaluation period.

Subject's compliance is derived as the farthest from 100% in absolute value between trifarotene 50 µg/g compliance and vehicle compliance.

Video compliance will be calculated on a per-subject basis as follows:

 $\label{eq:Video} \mbox{Video Compliance} = 100 \frac{\mbox{Actual Videos}}{\mbox{Planned Videos} - \mbox{Missed Videos due to Prescribed Dose Reductions}}$ 

Planned videos are calculated as the number of days between start date and stop date of each compliance evaluation period.

Treatment compliance will be summarized at each analysis visit and overall using descriptive statistics (n, mean, standard deviation, median, first and third quartile, min and max) by treatment side (trifarotene 50  $\mu$ g/g versus vehicle) and overall in the ITT population.

Frequencies and proportions (n, %) of subjects with treatment compliance <80%, between 80% and 120% and >120% will be summarized at each analysis visit and overall by treatment side

(trifarotene 50 µg/g versus vehicle) and overall in the ITT population.

Video compliance will be summarized at each analysis visit and overall using descriptive statistics (n, mean, standard deviation, median, first and third quartile, min and max) in the ITT population.

Frequencies and proportions (n, %) of subjects with video compliance <80%, between 80% and 120% and >120% will be summarized at each analysis visit and overall in the ITT population.

Treatment compliance, video compliance and drug accountability will be presented in listings.

### 6.2.7.3 Prescribed Dose Reductions

Descriptive statistics (n, mean, standard deviation, median, first and third quartile, min and max) or frequencies and proportions (n, %) of subjects for each classification category (as applicable) will be presented at each analysis visit for drugs in the ITT population for the following:

- Subjects with Prescribed Dose Reduction since the Last Scheduled Visit
- Reasons for Prescribed Dose Reduction
- Application/Dose Frequency during the Prescribed Dose Reduction
- Duration of Prescribed Dose Reduction (days)
- Missed Applications due to Prescribed Dose Reductions

Duration of the prescribed dose reduction will be calculated as Dose Reduction End Date minus Dose Reduction Start Date plus one (1).

Listings for drugs prescribed dose reductions will be provided.

### **6.2.7.4** Non-Investigational Products

Frequencies and proportions (n, %) of subjects using any non-investigational products during the study will be summarized by treatment side (trifarotene 50  $\mu$ g/g versus vehicle) in the ITT population.

All non-investigational products used during the study will be listed.

### 6.3 Efficacy Analysis

Primary inference for efficacy analysis will be based on the ITT population at week 24.

Subjects will be summarized and analyzed according to the treatment sides they were randomized to and all efficacy data (including efficacy data of incomplete treatments) will be listed.

### **6.3.1** Missing Data Pattern

Distinct missing data patterns of acne atrophic scar counts with their corresponding frequencies

1.0

CONFIDENTIAL

Page 45 of 59 Final version 2.0, 27FEB2023

[figure not shown]
and proportions (n, %) of subjects will be presented for each treatment side (trifarotene 50  $\mu$ g/g versus vehicle) in order to establish whether they are monotone or non-monotone.

### 6.3.2 Efficacy Data Summary

**Study Number 202395** 

Statistical Analysis Plan

A summary based on observed case (OC) will be provided for all primary and secondary efficacy endpoints and Quality of Life/Subject-Reported Outcomes. For these summaries, no data will be imputed.

### 6.3.3 Analysis of Primary Endpoint

The hypothesis test for the primary endpoint can be formally defined as follows:

$$\begin{cases} H_0: \mu_{Diff} = 0 \\ H_a: \mu_{Diff} \neq 0 \end{cases}$$

where  $\mu_{Diff}$  is the mean of the differences in change from baseline in total atrophic acne scar count at Week 24 between the trifarotene 50  $\mu$ g/g side and the vehicle side.

The hypothesis test for the primary endpoint will be evaluated on the ITT population at the two-sided significance level  $\alpha = 0.05$ . Efficacy will be claimed if the between treatment difference on the primary endpoint is statistically significant with a p-value < 0.05.

The bilateral difference between the trifarotene side and the vehicle side in absolute change from baseline in total atrophic acne scar counts at Week 24 will be analyzed on the ITT population using the Student's t-test for paired samples. The point estimate of the mean difference and the related 95% confidence interval will be presented. Assumption of normality will be checked. If normality assumption is not met, the appropriate non-parametric statistical method (Wilcoxon signed rank test, Hodges-Lehmann estimate of location shift and asymptotic confidence interval) will be used.

For analysis of change from baseline in total atrophic acne scar counts to Week 24, missing counts will be imputed using Multiple Imputation (MI) under the Missing At Random (MAR) assumption. It is expected that the pattern of missing data will be monotonic, with slight deviations being corrected by the Markov Chain Monte Carlo (MCMC) method of the SAS MI procedure. Separate imputations by treatment group will be carried out. Linear regression will be employed to model the missing acne counts, with the following covariates included in the imputation model: non-missing total atrophic acne scar counts from earlier time points (see Section 6.3.6.2 for further details).

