5.4.3 Study Drug Application with Video Collection

NOTE: At the Baseline visit, the subject will apply study drug to each side of the face under site staff supervision, to ensure proper use. The subject will be instructed not to apply study drug on the first evening.

The subject will apply the proper study drug on each half-face once a day (evenings): chin, cheek, nose and forehead (avoiding application in/close to eyes, angles of the mouth, lips and mucous membranes). Refer to Figure 1 for study drug application.

The objective is to cover each **COL** with a thin layer of the proper study drug, even on areas on the face with no clinically evident acne (no spot or localized treatment). One pump actuation should be enough to cover the forehead, cheek, nose, and chin. Avoid application in/close to eyes, or angles of the mouth, lips and mucous membrane.

The study drug should not be applied to cuts, abrasions, eczematous, or sunburned skin.

Each evening, subjects will collect a video of applying the study drug, as follows:

- 1. Have the study drug available and the electronic tablet ready for use
- 2. Wash hands
- 3. Wash the entire face with Cetaphil Gentle Skin Cleanser or approved cleanser
- 4. Pat dry the face
- 5. Begin recording with the study electronic tablet
- 6. Follow instructions for applying the proper study drug to the RIGHT side of the face
 - a. Briefly video the study drug container and label, to document which product was applied
 - b. Apply a thin layer of study drug to the entire RIGHT face (forehead, nose, cheek, chin). DO NOT SPOT APPLY
 - c. One pump actuation should be adequate
 - d. Avoid eyes, lips and mucous membranes
- 7. Wash hands
- 8. Follow instructions for applying the proper study drug to the LEFT side of the face.

- a. Briefly video the study drug container and label, to document which product was applied.
- b. Apply a thin layer of study drug to the entire LEFT face (forehead, nose, cheek, chin). DO NOT SPOT APPLY
- c. One pump actuation should be adequate
- d. Avoid eyes, lips and mucous membranes
- 9. Stop video recording (and follow further instructions associated with the electronic tablet)

The video capture of study drug use will be used as supportive evidence of treatment compliance (Section 5.4.6.5 - Treatment Compliance – Supportive Video Evidence).

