5.4.6.2 Study Drug Shipment and Accountability

The drug depot will ship appropriate quantities of study drug kits to each site, based upon individual site needs and within whole block sizes, as specified per the randomization list.

Upon receipt, the site must conduct a complete inventory of all study drug kits. If a damaged shipment is received and/or a temperature excursion has been experienced, the site will notify the Sponsor/CRO and follow the guidelines according to the current version of the pharmacy manual.

All study drug sent to the Investigator/Institution will be accounted for and no unauthorized use is permitted. Subjects will be instructed to return all study drug and the study electronic tablet per the Schedule of Assessments (Section 5.1.2).

The investigator or designee will maintain accurate records of supplies received, inventoried at the clinical study site and used per subject. Used and unused study drug will be appropriately reconciled by the monitor and returned to the Sponsor or designee for destruction as instructed by the Sponsor (Section 5.4.6.3 – Dispensing and Return of Study Drug).

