### 3.3.2 Method of Assigning Subjects to Treatment Sides

Upon signature of the ICF, each subject will be assigned a Subject Identification Number (SIN) to be used throughout the study. Once a SIN has been assigned, that number must not be used again for any other subject. Subjects may be re-screened once provided the reason for re-screening is not related to atrophic scar counts, acne severity (IGA) or lesion counts.

0

Study Number 202395 Statistical Analysis Plan CONFIDENTIAL

Page 20 of 59 Final version 2.0, 27FEB2023

Prior to the start of the clinical study, a randomization list will be generated and transmitted to the clinical packaging organization for study drug labeling. The randomization will assign the trifarotene (CD5789) cream or trifarotene vehicle cream to the right or left side of the face, for each study drug kit, and study drug instructions will include which study drug should be applied on which side of the face.

NOTE: For the purposes of this protocol, the "left" or "right" side of the face is always defined as the subject's left or right.

Upon chronological order of confirming subject eligibility, subjects are assigned a study drug kit in ascending numerical order of kit ID.

Refer to section 3.1.1 for an illustration of the study design and treatment allocation.

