### 6.3.6 Statistical/Analytical Issues

### **6.3.6.1** Adjustments for Covariates

No adjustment for covariates is planned for the primary, secondary and exploratory efficacy analyses.

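### The primary paired t-test has no term for the randomised side; adding one is a nearly free efficiency safeguard, and leaving it out is not an error

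*SAP*

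**What the plan says.** The only randomised factor is laterality. SAP 3.3.2 (matching protocol 5.4.7) states: "The randomization will assign the trifarotene (CD5789) cream or trifarotene vehicle cream to the right or left side of the face". The list is evidently blocked, because protocol 5.4.6.2 has kits shipped "within whole block sizes, as specified per the randomization list". Block size and left:right ratio are not stated in the available text.

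The two sides are handled in a fixed order. In protocol 5.4.3 each evening's application begins with the instruction "Follow instructions for applying the proper study drug to the RIGHT side of the face", then hand washing, then the left side.

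The primary analysis variable in SAP 6.3.3 is "The bilateral difference between the trifarotene side and the vehicle side in absolute change from baseline in total atrophic acne scar counts at Week 24", which "will be analyzed on the ITT population using the Student's t-test for paired samples". SAP 6.3.5.1 applies the same test at Weeks 1 to 20, and SAP 6.3.6.5 places those seven tests in a fixed sequence from Week 20 back to Week 1. SAP 6.3.6.1 adds: "No adjustment for covariates is planned for the primary, secondary and exploratory efficacy analyses". None of the four sensitivity analyses in SAP 6.3.4 uses side.

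**The concern.** Side in this design plays the part that period plays in a two-period crossover. If change differs between left and right for reasons unrelated to product, each paired difference is centred on tau + g or tau - g, depending on where trifarotene was assigned. Blocking keeps the two assignment groups close to equal, so g largely cancels from the mean. The paired t-test nevertheless counts the spread between the two groups as noise.

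What is at stake is precision: a wider interval than necessary for the primary endpoint and for each step of the hierarchy, where one failure stops all later testing. There is also a smaller point. If the groups are unequal in the realised sample, part of g stays in the estimate for that sample. About 25 sites for 118 subjects is 118/25, or roughly 4.7 per site, so incomplete blocks are plausible.

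**Working it through.** **Inputs.** From SAP section 4 and Table 8 (protocol 7.2 agrees): mean difference -1.7, SD of the difference 6.0, two-sided alpha 0.05, power 80%, 100 evaluable pairs, 15% drop-out, 118 randomised. From SAP 4.1: maximum N of 160, re-estimation after 40 subjects. The documents give no value for g, so a range of 0 to 3 scars is assumed, with 1:1 side allocation, normal differences and a g common to all subjects.

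**Step 1: the plan's own figure.** n >= (t[0.975, n-1] + t[0.80, n-1])² × 6.0² / 1.7². At n = 100 the right-hand side is (1.984 + 0.845)² × 36 / 2.89 = 99.7, so n = 100. Then 100 / 0.85 = 117.6, giving 118. Both figures reproduce. Noncentral-t power at 100 pairs is 80.1%.

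**Step 2: the model.** D_i = tau + g·z_i + e_i, with z = +1 if trifarotene is on the left and -1 if on the right. At 1:1 allocation, Var(D) = Var(e) + g². The paired t-test uses Var(D) on n - 1 degrees of freedom. The side-adjusted estimate is the average of the two group means and uses Var(e) on n - 2.

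**Step 3: interval width.** SAP section 4 applies 6.0 to the unadjusted difference, so total SD is held at 6.0 and the residual SD is sqrt(36 - g²). The planned half-width is 1.984 × 6.0 / 10 = 1.191 scars. With a side term it is 1.984 × sqrt(36 - g²) / 10:

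| g (scars) | Residual SD | Half-width | Change | Power |
|---|---|---|---|---|
| 0 | 6.000 | 1.191 | +0.01% | 80.1% |
| 0.5 | 5.979 | 1.187 | -0.3% | 80.4% |
| 1 | 5.916 | 1.174 | -1.4% | 81.2% |
| 1.7 | 5.754 | 1.142 | -4.1% | 83.3% |
| 2 | 5.657 | 1.123 | -5.7% | 84.5% |
| 3 | 5.196 | 1.031 | -13.4% | 90.0% |

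A 5% narrower interval needs g of about 1.9 scars, which is more than the 1.7-scar treatment effect.

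**Step 4: validity of the planned test.** In simulation (40,000 runs, 100 pairs, total SD 6.0) the paired t-test shows no bias at g = 0, 1, 2 or 3. With exactly balanced sides its type I error is 5.2%, 4.6%, 3.8% and 2.4% in that order; the first is 5% within simulation error. With unblocked side assignment its coverage is nominal at every g.

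**Step 5: the blinded re-estimation.** SAP 4.1 estimates the variance as n1/(n1 - 1) times the mean squared left-right difference. Read as the difference in change from baseline, that quantity contains g². The planned unadjusted test was simulated under this rule (first 40 pairs, floor 100, cap 160, N read as evaluable pairs, residual SD 6.0). Power stays at about 83% to 84% for g from 0 to 3. Mean N rises from about 115 at g = 0 to about 133 at g = 3.

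**Step 6: unequal allocation.** For illustration, a 65/53 split shifts the unadjusted estimate by (65 - 53)/118 × g = 0.10g. At g = 2 that is 0.2 scars, or 12% of 1.7. The side term removes this shift.

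**The case against.** The strongest objection is that nothing in the documents points to a non-zero g. Application order is the only systematic asymmetry described, and no effect on scars is attributed to it. Influences that vary from subject to subject, such as handedness or sleeping side, would be only partly captured by a term common to all. For modest g the gain is negligible, and it becomes material only when the side effect exceeds the drug effect. All of this stands.

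It also stands that sizing and analysis are consistent with each other. The SD of 6.0 refers to the unadjusted difference, and the re-estimation responds to g². Adding g² on top of 6.0 at a fixed 100 pairs would suggest lost power, but that overlooks the re-estimation.

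Two stronger readings are tempting and are not supported. A reader might infer that the test disregards the randomisation. It does not, because the assignment determines which half-face counts as trifarotene. A reader might also infer that the primary interval is too wide as a matter of fact. That holds only if g is not zero, and the conservatism further depends on near-balanced allocation.

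Finally, the change is not confined to the SAP. The paired t-test is named in protocol 7.4.3.1 and 7.4.3.2, and the planned Wilcoxon signed-rank fallback would need a matching form. That is a fair cost, and the fix provides for it.

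**Conclusion.** The primary and hierarchical tests are valid as planned: unbiased over randomisation, with type I error at or below 5%. What is missing is a side term that would follow the randomisation and protect precision if a systematic left-right difference exists. The benefit is conditional and usually small: nothing at g = 0 and about 1.4% of interval width at g = 1, rising to 5.7% at g = 2. Without the term, a large g would mainly cost additional subjects through the re-estimation.

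These figures rest on 1:1 side allocation, normal differences, a constant g and an assumed range for g. The change is still worth making because it uses data already held, costs almost nothing when g is zero and removes any shift from unequal side allocation. It is an efficiency improvement, not the correction of an error.

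**What to change.** - In SAP 6.3.3 and 6.3.5.1, prespecify D_i = tau + g·z_i, with z = +1 or -1 by randomised side. Test tau in each imputed dataset, pool with PROC MIANALYZE as planned, and report the estimate of g with its interval. Keep the plain paired t-test as a supportive analysis in SAP 6.3.4.
- Align the non-parametric fallback. Compare left-minus-right change between the two assignment groups by a rank-sum test. The groups are centred on g + tau and g - tau, so their shift is 2·tau; report the Hodges-Lehmann shift divided by 2.
- Mirror the wording in protocol 7.4.3.1 and 7.4.3.2, and state the left:right ratio and, once disclosure no longer threatens concealment, the block size.

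The cost is one degree of freedom, one model line and a protocol wording change. No new data are needed, since the assigned side is already in the randomisation list. If the sponsor prefers not to change the primary test, adding the side-adjusted model to SAP 6.3.4 as a supportive analysis would still make g visible.
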